6.3 Subject Exclusion Criteria

1. Currently participating and receiving another study therapy or has participated in a study of an investigational agent and received study therapy or used an investigational device within 4 weeks of the first dose of treatment.
2. Prior radiation therapy precluding SBRT

3. Continuous oxygen use
4. Current use of immunosuppressive medication, EXCEPT for the following: a. intranasal, inhaled, topical steroids, or local steroid injection (e.g., intra-articular injection); b. Systemic corticosteroids at physiologic doses \leq 10 mg/day of prednisone or equivalent; c. Steroids as premedication for hypersensitivity reactions (e.g., CT scan premedication).
5. Active autoimmune disease that might deteriorate when receiving an immuno-stimulatory agent. Patients with diabetes type I, vitiligo, psoriasis, or hypo- or hyperthyroid diseases not requiring immunosuppressive treatment are eligible. Replacement therapy (e.g. thyroxine, insulin, or physiologic corticosteroid replacement therapy for adrenal or pituitary insufficiency) is not considered a form of systemic treatment.
6. Known prior severe hypersensitivity to investigational product or any component in its formulations, including known severe hypersensitivity reactions to monoclonal antibodies (NCI CTCAE v4.03 Grade \geq 3)
7. Patient who rapidly progressed on prior immunotherapy, as determined by the treating physician, are not eligible.
8. Prior Therapies:
 - a. Treatment with a monoclonal antibody within 4 weeks prior to study Day 1 or has not recovered (i.e., \geq Grade 1 at baseline) from adverse events due to agents administered.
 - b. Prior chemotherapy, targeted small molecule therapy, within 4 weeks prior to study Day 1 or has not recovered (i.e., \geq Grade 1 at baseline) from adverse events due to a previously administered agent (excluding Grade 2 neuropathy).
 - c. Prior therapy with an anti-PD-1, anti-PD-L1, anti-PD-L2, anti-CD137, or anti-Cytotoxic T-lymphocyte-associated antigen-4 (CTLA-4) antibody (including ipilimumab or any other antibody or drug specifically targeting T-cell co-stimulation or checkpoint pathways) within 4 weeks prior to study Day 1 or has not recovered (i.e., \geq Grade 1 at baseline) from adverse events.
9. Comorbidities or Prior Conditions:
 - a. Known psychiatric or substance abuse disorders that would interfere with cooperation with the requirements of the trial.
 - b. Prior organ transplantation including allogenic stem-cell transplantation.
 - c. Known additional malignancy that is progressing or requires active treatment. Exceptions include basal cell carcinoma of the skin, squamous cell carcinoma of the skin, or in situ cervical cancer that has undergone potentially curative therapy.
 - d. Known history of active TB (Tuberculosis).
 - e. Known history of HIV or known acquired immunodeficiency syndrome.
 - f. Active Hepatitis B virus (HBV) or Hepatitis C virus (HCV) infection at screening or positive serologies indicating prior infection.
 - g. Active infection requiring systemic therapy.

- h. Evidence of interstitial lung disease or active, non-infectious pneumonitis.

- i. Clinically significant (i.e., active) cardiovascular disease: cerebral vascular accident/stroke (< 6 months prior to enrollment), myocardial infarction (< 6 months prior to enrollment), unstable angina, congestive heart failure (\geq New York Heart Association Classification Class II), or serious cardiac arrhythmia requiring medication.
- 10. Pregnant women or women who are breastfeeding or of childbearing potential and not using a highly effective method of birth control for at least one month prior to enrollment. If the risk of contraception exists, male and female subjects must use highly effective contraception throughout the study and for at least 60 days after last avelumab treatment.
 - a. Highly effective contraception includes either 2 barrier methods (diaphragm, condom by the partner, copper intrauterine device, sponge, or spermicide), or 1 barrier method and 1 hormonal method (any oral, subcutaneous, intrauterine, or intramuscular registered and marketed contraceptive agent that contains an estrogen and/or a progesterone agent).
- 11. Vaccination within 4 weeks prior to the first dose of avelumab and while on trial is prohibited except for administration of inactivated vaccines.
- 12. Concomitant use of the following medications
 - a. Any investigational anticancer therapy.
 - b. Any concurrent chemotherapy, immunotherapy, or biologic therapy. Concurrent use of hormones for non-cancer-related conditions (e.g., insulin for diabetes and hormone replacement therapy) is acceptable.
 - c. Immunosuppressive medications including, but not limited to systemic corticosteroids (>10 mg/day prednisone or equivalent), methotrexate, azathioprine, and tumor necrosis factor alpha (TNF- α) blockers. Use of immunosuppressive medications for the management of investigational product-related AEs, in subjects with contrast allergies is acceptable. In addition, use of inhaled and intranasal corticosteroids is permitted.
- 13. Known contraindications to radiotherapy

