Exclusion Criteria (summarized)	
1. Currently participating and receiving another study therapy or has participated in a study of an investigational agent and received study therapy or used an investigational device within 4 weeks of the first dose of treatment.2. Continuous oxygen use3. Known history of active TB (Tuberculosis), HIV, and/or Hepatitis B/C4. Hypersensitivity to avelumab or any of its excipients5. Prior monoclonal antibody treatment within 4 weeks prior to study Day 1 or has not recovered (i.e., \geq Grade 1 at baseline) from adverse events due to agents administered > 4 weeks earlier.6. Prior chemotherapy, targeted small molecule therapy, within 4 weeks prior to study Day 1 or has not recovered (i.e., \geq Grade 1 at baseline) from adverse events due to a previously administered agent (excluding Grade 2 neuropathy).7. Prior therapy with an anti-PD-1, anti-PD-L1, anti-PD-L2, anti-CD137, or anti-Cytotoxic T-lymphocyte-associated antigen-4 (CTLA-4) antibody (including ipilimumab or any other antibody or drug specifically targeting T-cell co-stimulation or checkpoint pathways) within 4 weeks prior to study Day 1 or has not recovered (i.e., \geq Grade 1 at baseline) from adverse events due to a previously administered agent
Study Drug	Avelumab; 10mg/kg delivered by IV infusion

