6.1 CRITERIA FOR SUBJECT ELIGIBILITY

6.2 Subject Inclusion Criteria

1. Patient willing and able to provide written informed consent for the trial.
2. Patient age ≥ 18 at time of consent.
3. Histologically or cytologically confirmed malignant pleural or peritoneal mesothelioma (MPM).
4. No plans for surgical resection.
5. At least one prior line of systemic therapy. Note: Patients on prior immunotherapy are eligible.
6. At least one targetable lesion appropriate for palliative SBRT and one non-target lesion
7. Karnofsky Performance Score (KPS) $\geq 70\%$
8. If of childbearing potential, must be willing to use highly effective mode of contraception for at least one month prior, during, and for 2 months after the end of active therapy
9. Adequate organ function, defined as
 - Absolute Neutrophil Count $\geq 1.5K/\text{mcL}$.
 - Platelet count $\geq 100K/\text{mcL}$.
 - Adequate renal function as defined by an estimated creatinine clearance $\geq 30 \text{ mL/min}$ according to the Cockcroft-Gault formula or serum creatinine $\leq 1.5 \times \text{ULN}$
 - Hemoglobin $\geq 9\text{g/dL}$ (prior transfusion permitted)
 - Total bilirubin level $\leq 1.5 \times$ the upper limit of normal (ULN) range
 - AST and ALT levels $\leq 2.5 \times \text{ULN}$ or AST and ALT levels $\leq 5 \times \text{ULN}$ (for subjects with documented metastatic disease to the liver).
10. If the patient received major surgery, they must have recovered adequately from the toxicity and/or complications from the intervention prior to starting therapy.

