9.4 Dose Modification and Discontinuation

9.4.1 Adverse Drug Reactions (ADRs) Requiring Avelumab Discontinuation or Dose Modification

Any Grade 4 ADRs require treatment discontinuation with avelumab except for single laboratory values out of normal range that are unlikely related to study treatment as assessed by the investigator, do not have any clinical correlate, and resolve within 7 days with adequate medical management.

Any Grade 3 ADRs require treatment discontinuation with avelumab except for any of the following:

- Transient (\leq 6 hours) Grade 3 flu-like symptoms or fever, which are controlled with medical management
- Transient (\leq 24 hours) Grade 3 fatigue, local reactions, headache, nausea, emesis that resolves to Grade \leq 1
- Single laboratory values out of normal range (excluding Grade \geq 3 liver function test increase) that are unlikely related to study treatment according to the Investigator, do not have any clinical correlate, and resolve to Grade \leq 1 within 7 days with adequate medical management
- Tumor flare phenomenon defined as local pain, irritation, or rash localized at sites of known or suspected tumor

Any Grade 2 ADR should be managed as follows:

- If a Grade 2 ADR resolves to Grade \leq 1 by the last day of the current cycle, treatment may continue.
- If a Grade 2 ADR does not resolve to Grade \leq 1 by the last day of the current cycle, infusions should not be given on the following cycle. If at the end of the following cycle the event has not resolved to Grade 1, the subject should permanently discontinue treatment with avelumab (except for hormone insufficiencies, that can be managed by replacement therapy; for these hormone insufficiencies, up to 2 subsequent doses may be omitted).
- Upon the second occurrence of the same Grade 2 ADR (except for hormone insufficiencies that can be managed by replacement therapy) in the same subject, treatment with avelumab will be permanently discontinued.

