13.1 CRITERIA FOR REMOVAL FROM STUDY

Patients should **permanently** discontinue treatment with avelumab for the reasons enumerated in Section 9 or in the event of:

- Intolerable adverse events (e.g. CTCAE v4.0 grade 3 or 4) that cannot be managed by dose modification or delay
- Further dose modification or delay considered necessary but not allowed per protocol section 9.4
- Pregnancy¹
- Withdrawal of informed consent²
- If the treating physician determines that it is in the best interest of the patient to stop study drug
- Non-compliance with the defined treatment plan

Patients will be removed from study after treatment ends in the event of:

- Death
- Pregnancy¹
- Withdrawal of informed consent²
- Non-compliance with the defined follow up studies

¹Pregnancy: In case of a patient or the patient's partner becoming pregnant during the trial the investigational drug has to be immediately stopped and the patients must be followed-up until birth or other termination of the pregnancy. Repeat counseling on birth defect risk must be offered.

²Consent withdrawal: in case a patient withdraws his/her consent for taking drug, it is of utmost importance for the robustness and integrity of the trial results that his/her safety data are recorded until the end of the 52 weeks period. Thus, all patients will be asked to follow their visit schedule until 52 weeks.

Patients who discontinue from this trial are not allowed to be reenrolled in this trial. Patients who discontinue medication within the first two weeks (during the washout period) will be replaced. For the patients who stopped trial before enrollment, their data will be part of the description of the screening population.

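### Exclusion 8c does not ask how severe an earlier, now resolved checkpoint-inhibitor toxicity was, so rechallenge after myocarditis or Grade 3-4 colitis, pneumonitis or hepatitis is not addressed

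*Combined protocol and SAP*

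**What the plan says.** **Entry.** Inclusion item 5 in Section 6.2 requires at least one prior line of systemic therapy and adds: "Note: Patients on prior immunotherapy are eligible". Section 6.3, item 8c, then restricts "Prior therapy with an anti-PD-1, anti-PD-L1, anti-PD-L2, anti-CD137, or anti-Cytotoxic T-lymphocyte-associated antigen-4 (CTLA-4) antibody". It excludes a patient treated within 4 weeks of Day 1, or with an adverse event still at Grade 1 or above at baseline. Item 7 of the exclusions summarized in Section 1.0 applies the same test: "within 4 weeks prior to study Day 1 or has not recovered". One other item in Section 6.3 looks back at earlier immunotherapy, and it concerns progression: "Patient who rapidly progressed on prior immunotherapy, as determined by the treating physician, are not eligible".

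**On study.** Section 9.4.1 says "Any Grade 3 ADRs require treatment discontinuation with avelumab except for any of the following", followed by a short list of transient or minor events, and "Any Grade 4 ADRs require treatment discontinuation with avelumab except for single laboratory values out of normal range" under stated conditions. The Section 9.5 tables discontinue avelumab for Grade 3-4 diarrhea/colitis, pneumonitis and liver test elevation, and discontinue it permanently for immune-mediated myocarditis. Section 13.1 says patients should permanently "discontinue treatment with avelumab for the reasons enumerated in Section 9".

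**The concern.** Once a patient is on avelumab, recovery from one of these four events does not bring the drug back. At entry, recovery plus four weeks is the whole test. Someone who recovered from checkpoint-inhibitor myocarditis or Grade 4 colitis can be given avelumab plus SBRT without any written rule on the matter, and the decision rests with the individual physician.

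The stake is that patient's safety. Pneumonitis shows why the combination matters: Section 11.1 names radiation pneumonitis as a primary toxicity of concern and also lists pneumonitis for avelumab, and Section 3.3 says no results yet exist from trials of radiotherapy combined with anti-PD-L1 treatment.

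**Working it through.** The plan states no figure on this point, so the main check compares the texts.

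**Step 1. Does any other entry criterion reach a fully resolved severe event?**

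| Criterion | What it covers | Reaches it? |
|---|---|---|
| 6.2 item 9 | Current organ function | No |
| 6.3 items 4, 12c | Current immunosuppression | No |
| 6.3 item 5 | Active autoimmune disease | No |
| 6.3 item 6 | Past Grade 3+ hypersensitivity | No; organ toxicity is not covered |
| 6.3 item 7 | Rapid progression on immunotherapy | No |
| 6.3 item 8a | Washout and recovery after any monoclonal antibody | No; same test as 8c |
| 6.3 item 9h | Interstitial lung disease, or pneumonitis that is active | No, unless lung changes remain |
| 6.3 item 9i | Active cardiovascular disease; myocarditis not listed | No, unless heart failure or treated arrhythmia remains |

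The pretreatment list in Section 8.1 includes a history and a 12-lead EKG but does not ask for the type or grade of earlier immune-related events.

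**Step 2. Do the on-study rules end avelumab for these events?**

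- Colitis and pneumonitis, Grade 3-4: Section 9.5 says discontinue, and the follow-up column has no instruction to resume. No exception in 9.4.1 fits.
- Liver test elevation, Grade 3-4: Section 9.5 says discontinue. The Grade 3 laboratory exception in 9.4.1 leaves out liver tests, and the Grade 4 exception applies only to values unlikely to be related to treatment.
- Immune-mediated myocarditis: Section 9.5 says discontinue permanently, without reference to grade.
- For the first three, permanence comes from Section 13.1, because the table rows themselves say only discontinue.

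**Step 3. How many patients might this concern?** The documents give neither the share of checkpoint-pretreated patients nor how many of them had one of the four events.

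Inputs:

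- Maximum enrollment: 27 (Section 1.0).
- Pretreated share s: assumed 10%, 25% or 50%.
- Event rate r, low: 1/53 = 1.9%. This assumes that one of the four Grade 3+ patients in the avelumab cohort of Section 3.2 had colitis, the only one of the four events named there. The split is not given.
- Event rate r, middle: 4/53 = 7.5%, all Grade 3+ treatment-related events in that cohort.
- Event rate r, high: 12%, the Grade 3+ rate Section 3.2 prints for pembrolizumab. It is printed beside 3 patients in a cohort of 38, and 3/38 would be 7.9%. I use 12% as printed because it gives the wider range.

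The middle and high rates count all event types, so they overstate the four events within those cohorts.

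Formulas: f = s × r; expected number = 27f; chance of at least one = 1 − (1 − f)^27.

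| s | r = 1/53 | r = 4/53 | r = 12% |
|---|---|---|---|
| 10% | 0.05; 5% | 0.20; 18% | 0.32; 28% |
| 25% | 0.13; 12% | 0.51; 40% | 0.81; 56% |
| 50% | 0.25; 23% | 1.02; 65% | 1.62; 81% |

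Each cell gives the expected number in 27, then the chance of at least one. Top corner: f = 0.50 × 0.12 = 0.06; 27 × 0.06 = 1.62; 1 − 0.94^27 = 0.81. The calculation ignores selection: a patient with a severe past event must also reach Grade 0 and be offered the trial, which would lower these numbers.

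**The case against.** The strongest reply is that the plan contains no error here. Section 9 governs a patient who reacts while taking avelumab. The patient at entry reacted to an earlier and often different agent, has been off it for at least four weeks, and must be at Grade 0, which is stricter than the Grade 1 level at which Section 9.5 often lets avelumab resume. Section 7.0 has an attending physician evaluate every patient, Section 11.1.1 sends events before the first dose to the medical history page, and 8c can hardly be applied without asking about earlier toxicity. The documents give no recurrence rate after rechallenge, so the hazard is argued by analogy only.

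Most of this stands and limits the point. A reader might infer that Sections 6.3 and 9 contradict each other; they do not, because they govern different situations. A reader might also infer that Section 9 treats every severe immune-related event as a lifetime bar. It does not: Section 9.5 allows avelumab to resume after Grade 3-4 rash improves, after Grade 3-4 endocrinopathy, after a Grade 3 creatinine rise, and after a first Grade 3 event of another type. The comparison holds for the four named events only.

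The reply does not supply a written rule. Physician judgment may well turn such a patient away, but nothing requires it, and no rationale is given for leaving the matter open. Item 6 shows that excluding on the grade of a past reaction is already part of this plan's approach.

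**Conclusion.** The gap is real and the change is worth considering as a low-cost patient-safety improvement. Applied exactly as written, the criteria admit a patient fully recovered from immune-mediated myocarditis or Grade 3-4 colitis, pneumonitis or hepatitis on a checkpoint inhibitor. That conclusion comes from the text and needs no assumption.

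The size does rest on assumptions. About 0.05 to 1.6 patients in 27 is an illustration across assumed pretreated shares and borrowed event rates. It bounds neither the risk nor the cost. A reader might infer that fewer than one patient would ever be affected; the high rate at a 50% share already exceeds that.

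A reader might also infer that the gap undermines the two-stage safety rule in Section 14.0. Any such figure would need a toxicity rate for rechallenged patients, which the documents do not give, so no effect on the rule is claimed.

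**What to change.** Add an exclusion 8d to Section 6.3, and the matching line to the summary in Section 1.0: *prior immune-mediated myocarditis of any grade, or prior Grade 3 or 4 immune-related diarrhea/colitis, pneumonitis or hepatitis (AST or ALT > 5 x ULN or total bilirubin > 3 x ULN), on a checkpoint inhibitor, even if resolved.* Add a matching line to the eligibility checklist, and record the type and highest grade of earlier immune-related events in the screening medical history.

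Keep the exclusion to these four events. A general bar on any other Grade 4 event, or entry versions of the two 12-week discontinuation triggers in Section 9.5, would go beyond what is shown here. Other resolved events stay under 8c, item 5 and the existing criteria.

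The administrative cost is one exclusion, one checklist line and one history entry. The real cost is that a few candidates are turned away from a rechallenge some clinicians would accept, in a disease for which Section 3.1 reports no FDA-approved second-line therapy. Over the illustrative range that is about 0.05 to 1.6 candidates in 27, or up to about 1.6 months of accrual at the planned one patient per month. If the sponsor prefers to allow rechallenge, the protocol should say so and state the conditions.

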7.0 RECRUITMENT PLAN

Eligible patients with malignant pleural or peritoneal mesothelioma will be recruited from the Thoracic Medical Oncology and Radiation Oncology departments at MSKCC. An attending physician of the Thoracic Medical Oncology and Radiation Oncology department will evaluate all patients. Participation is voluntary. The consenting physician will inform patients of their diagnosis, current treatment options, including standard treatment, and the risks, benefits and experimental nature of this treatment program.

Memorial Hospital is a major referral center for MPM. In addition, the study information may be placed on the institutional hospital website to maximize recruitment.

Patients under the age of 18 are excluded because this disease does not occur in patients that age, and the safety of these treatments has not been established for them. The

patient population includes all patients under the care of attending surgical, medical and radiation oncologists at MSKCC main campus or regional sites. Every attempt will be made to recruit women and minorities to participate in this study. There are no genders or racial restrictions.

8.1 PRETREATMENT EVALUATION

To be completed within 45 days prior to starting avelumab unless otherwise specified :

1. Signed informed consent for study participation
2. FDG-PET scan
3. CT of the chest, abdomen, and pelvis, preferably with contrast. The companion CT scan from the above FDG-PET scan may fulfill this requirement.
4. MRI of the lesion to be irradiated according to the following guidelines in the MSKCC Department of Radiation Oncology
 - a. Contraindication to MRI (i.e. pacemaker) = no participation in MRI component.
 - b. Contraindication to contrast only = MRI w/o contrast
 - c. No contraindication = MRI with contrast
5. 12-lead Electrocardiogram (EKG)
6. History and physical examination, including height, weight, vital signs (temperature, pulse rate, respiration rate, blood pressure), and performance status (Karnofsky)
7. Serum or urine pregnancy test for all women of childbearing potential (serum pregnancy test within 14 days or urine pregnancy test within 24 hours of starting avelumab)
8. CBC with differential and platelet count, CMP (including Na, Cl, BUN, Creatinine, K, CO₂, glucose, AST, ALT, alkaline phosphatase, total bilirubin, calcium, albumin, and total protein)
9. Free T4 and TSH
10. Serology for HEP BsAg, HBcAb and hepatitis C antibody within 30 days prior to starting avelumab
11. Baseline blood test for research purposes (See Section 10.4)
12. Tumor biopsy for confirmation of either progressive or metastatic disease completed as standard of care of two lesions, a lesion to be irradiated and a lesion to be un-irradiated. Biopsy to be core needle biopsy up to 4 cores, 1 core to be sent to pathology and 3 cores to be sent to lab for research for each site, preferably 18-gauge or larger, specified prior to biopsy, permanently fixed, managed by CSP, Correlative Science Program.

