12.0 CRITERIA FOR THERAPEUTIC RESPONSE/OUTCOME ASSESSMENT

For the purposes of this study, patients will be evaluated for response every 2 months after completing SBRT (approximately 8 weeks, or every 4 cycles). Modified RECIST for mesothelioma and RECIST 1.1 criteria will be used [22]. CT scan of the chest, abdomen, and pelvis will be used for response assessment. The companion CT from an integrated PET/CT examination is suitable for this requirement. As part of the secondary endpoints, progression-free and overall survival will be recorded. Progression-free survival is defined as the length of time from the start of active treatment (avelumab) until removal from study due to progressive disease (defined by modified RECIST 1.1) or death. Removal from study due to toxicity will be counted as censoring. Overall survival is defined as the length of time from the start of active treatment until d e a t h .

Modified RECIST for Mesothelioma [23, 24]

The modified RECIST criteria for mesothelioma use unidimensional measurements of tumor thickness perpendicular to the chest wall or mediastinum. In our protocol, the irradiated lesion is not required to be intrathoracic. This is measured on CT scan in 2 sites at 3 different levels at least 1cm apart. At reassessment, the thickness must be measured at the same position and level. Exhaustive documentation of non-measurable lesions are not required. The sum of tumor diameters is used to measure response.

Definitions of Overall Response	
Complete Response (CR)	Disappearance of all target lesions who no evidence of tumor elsewhere.

Partial Response (PR)	At least a 30% decrease in the sum of diameters of target lesions, taking as reference the baseline sum diameters.
Stable Disease (SD)	Response neither meeting the criteria of CR, PR or PD
Progressive Disease (PD)	At least a 20% increase in the sum of diameters of tumor measurements over the nadir measurement, or appearance of one or more new lesions.

RECIST 1.1

Evaluation of target lesions	
Complete Response (CR)	Disappearance of all target lesions Any pathological lymph nodes (whether target or non-target) must have reduction in short axis to <10 mm.
Partial Response (PR)	At least a 30% decrease in the sum of diameters of target lesions, taking as reference the baseline sum diameters.
Stable Disease (SD)	Neither sufficient shrinkage to qualify for PR nor sufficient increase to qualify for PD, taking as reference the smallest sum of diameters while on study.

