14.0 BIOSTATISTICS

The primary endpoint, the safety of a combination of avelumab and SBRT, will be defined based on the rate of any grade 3 or higher non-hematologic toxicity within the first 3 months after SBRT (for the rest of the section this will be referred to as AE). A two-stage stopping rule will be used to protect patients' safety. If 3 or more among the first 13 patients develop AEs, then the trial will be stopped and declared unsafe. Otherwise, an additional 14 patients will be enrolled and treated. If, among the total 27 patients, 5 or more patients are observed to have AEs, then the trial will also be declared unsafe. This stopping rule has a power of 80% declaring the true AE rate of 0.1 or lower safe, and a type 1 error rate (alpha) of 5% declaring true AE rate of 0.3 or higher safe.

For secondary endpoints, the overall response and the irradiated lesion and non-irradiated lesion response rates (4 months from start date of the combined therapy) based on RECIST 1.1 response criteria will be summarized by sample proportions and their confidence intervals. PFS and OS will be evaluated by Kaplan-Meier method.

For the exploratory objectives, we will evaluate changes of T-cell infiltration and serum immunophenotype at baseline and after SBRT + immunotherapy both in- and outside the irradiated field. The former is measured as numerical values so we will use Wilcoxon signed-rank test. The latter is categorical so we will tabulate it and employ the marginal homogeneity test. Due to the expected small sample size, results will be interpreted cautiously. The imaging studies using DWI-MRI and DCE-MRI, and FDG-PET will be correlated with biopsy results by McNemar's tests.

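### Baseline scans and biopsies may be taken up to 17 days before the required washout begins, so response and T-cell change can be measured from an on-treatment baseline

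*Combined protocol and SAP*

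**What the plan says.** Section 8.1 lists the baseline procedures under a single rule: "To be completed within 45 days prior to starting avelumab unless otherwise specified". Some items have a tighter limit. One is "Serology for HEP BsAg, HBcAb and hepatitis C antibody within 30 days prior to starting avelumab"; another is the pregnancy test (14 days for serum, 24 hours for urine). A calendar footnote in Section 10.1 puts research blood within 3 days before avelumab. CT, FDG-PET, MRI and the two-site biopsy keep the full 45 days.

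The washout is in Section 6.3, item 8, and is 4 weeks for each class of prior systemic therapy:
- 8a: "Treatment with a monoclonal antibody within 4 weeks prior to study Day 1 or has not recovered"
- 8b: "Prior chemotherapy, targeted small molecule therapy, within 4 weeks prior to study Day 1 or has not recovered"
- 8c, for agents "specifically targeting T-cell co-stimulation or checkpoint pathways) within 4 weeks prior to study Day 1"

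The baseline is then used as a reference in two places. Section 12.0 defines partial response as "At least a 30% decrease in the sum of diameters of target lesions, taking as reference the baseline sum diameters". Section 14.0 says "we will evaluate changes of T-cell infiltration and serum immunophenotype at baseline and after SBRT + immunotherapy", with a Wilcoxon signed-rank test for T-cell infiltration.

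**The concern.** The window for the reference measurements is longer than the time the patient must have been off the previous drug. A patient can be scanned and biopsied on day -45, receive the old drug until day -29, and still satisfy every written criterion.

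If the old drug was still shrinking disease, part of that shrinkage is counted as response to avelumab plus SBRT. If disease was growing through it, a real response is harder to reach. A baseline biopsy taken under chemotherapy or an earlier checkpoint inhibitor mixes the withdrawal of that drug into the paired T-cell change. With a single arm, no control group exists in which the carry-over would cancel. Once avelumab has started, a clean baseline cannot be recovered.

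**Working it through.** **1. The plan's own figure.** Section 14.0 gives operating characteristics for the safety rule: 13 + 14 patients, unsafe at 3 or more of 13 or at 5 or more of 27. The probability of declaring the regimen safe is the sum over x = 0, 1, 2 of P(Bin(13, p) = x) × P(Bin(14, p) ≤ 4 - x). At p = 0.1 this is 0.809, against 80% stated. At p = 0.3 it is 0.047, against 5% stated. The figures reproduce. They use only toxicity counts, so no baseline scan or biopsy enters them.

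**2. The overlap.** The screening window is 45 days (Section 8.1) and the washout is 4 weeks = 28 days (Section 6.3). 45 - 28 = 17 days, namely days -45 to -29, or 17/45 = 38% of the window.

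**3. Does anything else close the gap?**
- Section 6.3, item 12 bars concurrent anticancer therapy. It does not place screening tests relative to the last prior dose.
- Section 6.2, item 5 asks for at least one prior line and admits prior immunotherapy. It does not require progression on that line. Section 6.3, item 7 excludes only rapid progression on prior immunotherapy.
- Section 8.1 says the biopsy confirms progressive or metastatic disease, so metastatic disease alone is enough.
- The Section 10.1 calendar shows the next CT, PET, MRI and biopsies about two weeks after SBRT. None is repeated before Cycle 1.

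Nothing closes it.

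**4. Possible size.** The documents give no rate of change, so g is an assumption: the change in tumour sum per 28 days, for a scan on day -45. The ratio of the Day 1 sum to the baseline sum is f = (1 + g)^(45/28). The shrinkage from the Day 1 size that scores as partial response is 1 - 0.70/f.

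| Assumed g per 28 days | f | Shrinkage from Day 1 needed for PR |
|---|---|---|
| -20% | 0.699 | none; f is already below 0.70 |
| -10% | 0.844 | 17% |
| 0% | 1.000 | 30% |
| +10% | 1.166 | 40% |

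The negative rows assume that the old drug's effect lasts the full 45 days. If it stopped at a last dose on day -29, 16 days after the scan, the exponent is 16/28. Then f = 0.942 at -10% (PR needs 1 - 0.70/0.942 = 26%) and f = 0.880 at -20% (PR needs 1 - 0.70/0.880 = 20%). The +10% row only shows that the sign can reverse; growth before Day 1 is not specific to being on the old drug.

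**5. Leverage.** With 27 patients in the denominator, one reclassified response moves ORR by 1/27 = 3.7 points. For scale, Section 3.2 cites 9.4% (5 of 53) for avelumab alone.

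**The case against.** The scenario is narrow. Section 18.1 puts consent before protocol procedures, so for a research biopsy the patient would have to consent, have two lesions sampled, and then receive another dose of the old drug. The biopsy's stated purpose makes that unlikely, though not impossible. A standard-of-care CT taken during the last cycle of the old drug is the more realistic case. Response rates are secondary and are reported as proportions with confidence intervals, with no decision attached. Section 14.0 itself promises caution with the exploratory results. Serum immunophenotype is largely protected if the 3-day footnote covers the baseline sample. All of this stands, and it limits how often and how much the gap matters. It does not close the gap.

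Three stronger readings are tempting, and the documents do not support them.
- A reader might infer that toxicity from the last prior cycle can slip past eligibility, because the screening CBC and CMP share the 45-day window. Exclusion 8 separately bars patients who have not recovered from prior-agent adverse events, and the calendar repeats these labs at Cycle 1. What remains is only that no section says whether the Cycle 1 values must meet inclusion 9.
- A reader might infer that the safety conclusion is at risk. The primary endpoint counts grade 3 or higher non-hematologic toxicity within 3 months after SBRT and does not use the baseline scan or biopsy.
- A reader might conclude that the whole window should be cut to 28 days. The documents give no basis for such a cap on PET, MRI or biopsies, and it could force a repeat two-site biopsy. The order relative to the last prior dose is what matters.

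**Conclusion.** The concern holds as a limited design gap. Followed exactly, the plan permits baseline CT, PET, MRI and biopsies during 17 days in which the patient may still be on the previous drug. It therefore permits response and paired T-cell change to be measured from an on-treatment baseline. The effect can go either way and arises only in patients tested before their last prior dose. The documents give neither its frequency nor its size, so the correct statement is that baselines can be distorted, not that they are. The table in the working is conditional on the assumed rates and on a scan at the earliest permitted day. At no residual effect there is no distortion. The secondary response rates and the exploratory tissue and imaging results are exposed; the primary safety endpoint, N = 27 and the error rates are not. The change is worth making because it is cheap and the loss cannot be repaired later.

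**What to change.** In Section 8.1 and the study calendar, keep the 45-day window and add that the baseline CT (the response reference), PET, MRI and baseline biopsies must be done after the last dose of any prior anticancer therapy.

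- **CT:** if the only available CT predates that dose, repeat the standard-of-care CT before Cycle 1 Day 1.
- **Biopsy:** do not repeat a biopsy for this reason. Flag any taken before the last prior dose. State in Section 14.0 that flagged biopsies are left out of the paired T-cell analysis, or that results are shown with and without them.
- **Minor clarification:** say whether the Cycle 1 CBC and CMP must meet inclusion 9.

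The cost is amendment wording, a few repeat CTs or later-scheduled biopsies, and possibly a few fewer biopsy pairs in an already small sample. The sample size and stopping rule do not change.
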